#### **6.1.6. Pooling of Sites**

Not applicable.

#### **6.1.7. Derived Variables**

- **Weight of IP (g)** = dispensed tube weight – returned tube weight.

- **Number of expected IP applications** = calculated as  $2 * (\text{last treatment date} - \text{first treatment date} + 1)$ .
- **Number of IP applications** = number of expected IP applications – missed IP applications as collected in the case report form (CRF). As the time of missing dose is not captured in the CRF, only the dates will be used in determining number of missed doses; if 2 records exist for the same date, that will be considered as 2 missed IP applications.
- **Days on IP** = Calculated as last treatment date – first treatment date + 1. For subjects who are missing the date of last study drug application, for any reason, the last known contact date from subject visits CRF will be used in the calculation of treatment duration.
- **BMI (kg/m2)** =  $(\text{weight in kg}) / [(\text{height in cm}/100)^2]$ . For all visits, baseline height will be used to derive BMI since height is collected only at baseline.
- **Change from baseline** = value at current time point – value at baseline.
- **Percent change from baseline** =  $(\text{value at current time point} - \text{value at baseline}) / \text{value at baseline}$ .
- **TEAE** = any AE with an onset date/time after the first application of IP. If time is unavailable, any AE occurring on or after the date of first application of IP will be considered treatment emergent.

#### 6.1.8. Data Adjustments/Handling/Conventions

Upon the sponsor discretion, only safety and limited efficacy will be presented in Clinical Data Interchange Standards Consortium (CDISC) datasets. Data not subject to analysis according to this plan will not appear in any tables or graphs or listings or the CDISC datasets.

Adverse events will be coded using the Medical Dictionary for Regulatory Activities (MedDRA) version 23.1 thesaurus.

A treatment-related AE to study drug is any AE with a relationship to the study drug of possibly, probably, likely, or missing.

A treatment-related AE to phototherapy treatment is any AE with a relationship to the phototherapy treatment of likely or missing.

For partial AE and medication start dates:

- If the year is unknown, then do not impute the date but assign a missing value.
- If the year is known, but the month or month and day is unknown, then:
  - If the year matches the year of first dose date and the end date (if present) is after first dose date, then impute as the month and day of the first dose date.

- Otherwise, assign 01 January.
- If the year and month are known, but the day is unknown, then:
  - If the month and year match the month and year of the first dose date, then impute as the day of the first dose date.
  - Otherwise, assign 01.

For partial AE and medication end dates:

- If the year is unknown, then do not impute the date but assign as missing value.
- If the year is known, but the month or month and day is unknown, then:
  - If the year matches the year of the last date of the study (date of last contact if subject lost to follow-up; date of completion or early termination otherwise), then impute as the month and day of the last date of the study.
  - Otherwise, assign 31 December.
- If the year and month are known, but the day is unknown, then:
  - If the month and year match the month and year of the last date of the study, then impute as the day of the last date of the study.
  - Otherwise, assign the last day of the month.

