### **9.1. Adverse Events**

All AEs, TEAEs, and SAEs will be coded using the MedDRA dictionary version 23.1.

A TEAE is defined as an AE with an onset date/time on or after the first application of IP. An overall summary of TEAEs will be provided; this will present number and percent of subjects who reported at least 1 of the following: TEAE (including all TEAEs, TEAEs by maximum severity, and related TEAEs to study drug and phototherapy), SAE, discontinued the study due to a TEAE, discontinued the study drug due to a TEAE, and discontinued the phototherapy due to a TEAE.

The number and percent of subjects reporting TEAEs, grouped by MedDRA system organ class (SOC) and preferred term, will be tabulated by severity or greatest relationship to study drug and treatment group. In the case of multiple occurrences of the same TEAE within the same subject, each subject will only be counted once for each preferred term. In addition, summary by greatest relationship to the phototherapy treatment will be tabulated similarly.

In the summaries showing severity and relationship to study medication the event with the maximum severity (mild < moderate < severe < life-threatening < death) will be reported. If a particular event is missing the severity, then the strongest possible severity will be assumed for analysis (severity = severe).

In the AE data listings, all AEs will be displayed. Any AEs that are treatment emergent will be flagged.

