## **9.7. Concomitant Medications**

Prior and concomitant medications will be summarized descriptively by treatment group, Anatomical Therapeutic Chemical (ATC) Class Level 4, and Preferred Term using counts and percentages.

Prior medications will be presented separately from concomitant medications. Medications that started before the first application of IP will be considered prior medications whether or not they were stopped before the first application of study drug. Any medications continuing or starting after the first application of study drug will be considered to be concomitant. If a medication starts before the first application of study drug and continues after the first application of study drug it will be considered both prior and concomitant.

Medications will be coded using WHODrug Enhance Global B3G, version September 2020.

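### The SAP's start-date rule for an unknown day has no end-date check, so a record that stopped before first dose in the same month gets a start after its stop

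*SAP*

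**What the plan says.** SAP section 6.1.8 sets the imputation rules under the lead-in "For partial AE and medication start dates". Two branches can place a start on the first-dose date.

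- **Month unknown, or month and day unknown.** The year must match the year of first dose, and a second condition applies: "the end date (if present) is after first dose date, then impute as the month and day of the first dose date". If either condition fails, the start becomes 1 January.
- **Only the day unknown.** If the "month and year match the month and year of the first dose date, then impute as the day of the first dose date". If they do not match, the start becomes the first of the month. The stop date is not consulted.

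The imputed start then determines classification.

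- For adverse events, SAP section 6.1.7 says that, when no time is available, "any AE occurring on or after the date of first application of IP will be considered treatment emergent". Section 9.1 agrees: "A TEAE is defined as an AE with an onset date/time on or after the first application of IP".
- For medications, SAP section 9.7 says: "Medications that started before the first application of IP will be considered prior medications". Concomitant status goes to those continuing, or starting, after first application.

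Nothing else in the SAP caps an imputed start at the recorded stop or overrides the result.

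**The concern.** The month-unknown branch recognises that a recorded stop can prove that a record belongs before treatment. The day-unknown branch drops that evidence. The better-documented record, with its month known, therefore gets the impossible date, while the poorer one is placed correctly before treatment.

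What is at stake is classification. An adverse event that was over before the first application would enter the treatment-emergent tables. A medication that was over before the first application would leave the prior table. Records that start after they stop would also appear in the listings and datasets. With efficacy reduced to descriptive F-VASI summaries (SAP section 8), safety and medication summaries make up most of what this study will report.

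**Working it through.** The SAP gives no figure to reproduce, so the check applies its rules literally.

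**Worked cases.** Assume, for illustration, a first dose on 15 June 2021. The day-unknown columns take a start known only as June 2021. The month-unknown column takes a start known only as 2021.

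| Recorded stop | Day-unknown rule as written | Month-unknown rule as written | Day-unknown rule with an on-or-after check |
|---|---|---|---|
| 5 June | 15 June, 10 days after the stop | 1 January | 1 June |
| 14 June | 15 June, 1 day after the stop | 1 January | 1 June |
| 15 June | 15 June | 1 January | 15 June |
| 20 June | 15 June | 15 June | 15 June |
| none | 15 June | 15 June | 15 June |

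The written rule fails in the first two rows. In the last two rows the written branches agree, and imputing to first dose is the usual conservative choice.

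**What follows for the 5 June record.**

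- As an adverse event: the imputed onset has no time, so the date-only rule in section 6.1.7 applies. An onset on the first-dose date is treatment-emergent, although the event ended ten days earlier.
- As a medication: a start on 15 June is not before first application, so the record is not prior. It is not continuing either. Section 9.7 does not say whether a same-day start counts as after, so the record is either concomitant or in neither table. Both are wrong.

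**All date combinations in a 30-day month.** Take every first-dose day d from 1 to 30, and every pair of true start and known stop days with start ≤ stop.

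- Total: 30 × (30 × 31 / 2) = 30 × 465 = 13,950.
- Stop before first dose: for each d there are d(d − 1)/2 pairs. Summed over d = 1 to 30, this is 31 × 30 × 29 / 6 = 4,495.
- As written, all 4,495 get a start of d, later than the stop. No other combination does, because a stop on or after d cannot precede a start of d.
- With the end-date check, those 4,495 get day 1, which cannot be later than the stop. The number in error falls to 0.

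These are possible combinations, not an expected frequency in the trial. The largest reversal, in a 31-day month, is 31 − 1 = 30 days.

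**Which records can be exposed.** The start, the stop and the first dose must all fall in one calendar month. For a drug with a washout of w days, the stop day can be at most d − w and must be at least 1.

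- w = 28 (4 weeks): d must be 29 to 31, and the stop must fall on days 1 to 3.
- w = 56 (8 weeks): d would have to be at least 57, which is impossible. The same holds for anything longer.
- w = 14 (2 weeks, strong CYP3A4 inhibitors and inducers only): possible when d is 15 or later.

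The washouts are those of Protocol Table 2. Protocol sections 1.3 and 5.1.1 show that medications and adverse events are recorded at Screening, up to 35 days before Day 1, so pre-treatment records can exist.

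**The case against.** The strongest defence is that imputing to first dose is deliberately conservative: when the onset is uncertain, count the event as on treatment. That stands when the stop is missing or falls on or after first dose, and the proposed change leaves those records alone. It does not cover a record whose known stop shows that it ended before treatment, and the month-unknown branch shows that the authors did not mean it to.

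Several limits on the consequences also stand.

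- **Adverse events.** Protocol sections 5.1.9 and 5.7.5 collect non-serious events only from first application; serious events are collected from consent. The schedule does mark adverse event assessment at Screening, so the route is open but narrow.
- **Washout drugs.** A reader might infer that drugs stopped for washout are the most exposed. Protocol Table 2 does not support this: most washouts are 4 weeks or longer, so a compliant stop rarely or never falls in the first-dose month.
- **Medication labels.** A reader might also infer that affected medications become concomitant. Section 9.7 does not settle that; what is certain is that they stop being prior.
- **Negative durations.** SAP sections 9.1 and 9.7 plan counts and percentages and do not summarise durations, so a reversed interval would show only in listings and datasets.

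**Conclusion.** The rule is wrong as written; this is not merely missing detail. Every record with an unknown start day in the first-dose month and a known stop before first dose is dated after its own stop and misclassified.

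The size is small. The exposed records are mainly short courses of medication begun and ended during screening, together with screening-period serious adverse events and any other events recorded then. The documents do not give their number, and nothing supports reading this as a material inflation of the treatment-emergent tables. SAP section 6 makes all analyses descriptive, so no test result can change; only treatment-emergent and medication counts and listings can.

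This assumes that the programming follows the SAP text literally and that an imputed date carries no time. It is a minor correction, worth making because the result is plainly impossible for the records concerned.

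**What to change.** In SAP section 6.1.8, add to the day-unknown start rule that the first-dose day is used only if the stop date, where recorded, falls on or after first dose; otherwise assign the first of the month.

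In the month-unknown branch, replace the condition that "the end date (if present) is after first dose date" with an on-or-after version. Copying the existing strict wording into the day-unknown rule would not do: an event that stopped on the first-dose day would be moved to the first of the month and, unless first dose was itself on the 1st, would cease to be treatment-emergent. Using on or after in both places makes the branches agree and keeps such an event treatment-emergent.

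The cost is one added clause and one changed word in the SAP, with the matching conditions in the code. No new data are needed. Records with a missing or later stop keep their present handling.

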## 7. Study Subjects and Demographics

### 7.1. Disposition of Subjects and Withdrawals

Disposition will include tabulations of the number of subjects randomized into each treatment group, the number of subjects who received treatment, subjects completing the study, tabulated reasons for discontinuation from the study overall and due to COVID-19 disruption, and number of subjects in each analysis population. Disposition will be summarized for all subjects who were entered into database by treatment group and overall.

### 7.2. Demographics and Other Baseline Characteristics

Summary statistics for age, age group ( age  $\leq$  30, age  $>$  30), gender (including child-bearing potential), race, ethnicity, height, weight, baseline disease characteristics (F-VASI, Fitzpatrick skin type), percent total BSA affected by vitiligo, percent BSA affected by vitiligo on face, and BMI will be presented by treatment group and overall.

For the continuous variables, the number of non-missing values and the mean, standard deviation, minimum, Q1, median, Q3, and maximum will be tabulated.

For the categorical variables, the counts and proportions of each value will be tabulated.

These analyses will be conducted for the Safety population.

### **7.3. Exposure and Compliance**

The number of IP applications by each subject based on diary data will be summarized using descriptive statistics appropriate for continuous variables.

The amount of IP used by each subject based on tube weight will be summarized descriptively by treatment group using continuous methods.

The number of days on IP will be summarized descriptively by treatment group using continuous methods.

## **8. Efficacy Analysis**

Due to the study termination, it was the sponsor decision to not execute any efficacy analyses. Though the protocol indicates primary and secondary endpoints, upon the sponsor decision only F-VASI summaries will be provided based on observed value. Hence, observed, change and percent change from baseline in F-VASI scores will be summarized descriptively by treatment group using ITT population.

## **9. Safety and Tolerability Analysis**

Safety will be evaluated from reported AEs, physical examinations, local tolerability assessments, and changes in 12-lead ECGs, clinical laboratory values, and vital signs/weight. No inferential statistical tests will be performed.

All safety analyses will be performed on the Safety population.

### **9.1. Adverse Events**

All AEs, TEAEs, and SAEs will be coded using the MedDRA dictionary version 23.1.

A TEAE is defined as an AE with an onset date/time on or after the first application of IP. An overall summary of TEAEs will be provided; this will present number and percent of subjects who reported at least 1 of the following: TEAE (including all TEAEs, TEAEs by maximum severity, and related TEAEs to study drug and phototherapy), SAE, discontinued the study due to a TEAE, discontinued the study drug due to a TEAE, and discontinued the phototherapy due to a TEAE.

The number and percent of subjects reporting TEAEs, grouped by MedDRA system organ class (SOC) and preferred term, will be tabulated by severity or greatest relationship to study drug and treatment group. In the case of multiple occurrences of the same TEAE within the same subject, each subject will only be counted once for each preferred term. In addition, summary by greatest relationship to the phototherapy treatment will be tabulated similarly.

In the summaries showing severity and relationship to study medication the event with the maximum severity (mild < moderate < severe < life-threatening < death) will be reported. If a particular event is missing the severity, then the strongest possible severity will be assumed for analysis (severity = severe).

In the AE data listings, all AEs will be displayed. Any AEs that are treatment emergent will be flagged.

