#### **6.3.1. Adverse Events**

All AEs occurring during the study will be recorded and classified on the basis of MedDRA terminology for the safety population. AEs will be summarized by treatment group, the number of subjects reporting AEs, system organ class, preferred term, severity, relationship, and seriousness.

Serious adverse events (SAEs) will be listed by subject. SAEs will be summarized by treatment group, severity, and relationship to study treatment. For AEs, each subject will be counted only once within a system organ class or a preferred term using the event with the greatest relationship and greatest severity.

All information pertaining to AEs noted during the study will be listed by subject, detailing the verbatim description given by the Investigator, preferred term, system organ class, start date, stop date, severity, action taken regarding IP, corrective treatment, outcome, and IP and/or phototherapy relatedness. The event onset will also be shown relative (in number of days) to date of first application.

In addition, a listing of subjects who prematurely discontinue from the IP due to adverse events will also be provided.

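### SAP 9.1 gives two conflicting rules for which event represents a subject in the table by relationship to study drug; one of them can only lower the related count

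*SAP*

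**What the plan says.** SAP 9.1 describes the table of TEAEs by MedDRA system organ class and preferred term. Subjects "will be tabulated by severity or greatest relationship to study drug and treatment group". When the same TEAE recurs in a subject, "each subject will only be counted once for each preferred term". For the device, a "summary by greatest relationship to the phototherapy treatment will be tabulated similarly".

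The next paragraph states an event-selection rule: "In the summaries showing severity and relationship to study medication the event with the maximum severity" is the one reported. It ranks severity from mild to death and sets a missing severity to severe.

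Three other statements bear on the point:

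- The overall TEAE summary in SAP 9.1 gives the "number and percent of subjects who reported at least 1 of the following", and the list includes TEAEs related to study drug and to phototherapy.
- SAP 6.1.8 defines relatedness broadly: "A treatment-related AE to study drug is any AE with a relationship to the study drug of possibly, probably, likely, or missing".
- Protocol 6.3.1 counts each subject once within a system organ class or preferred term, "using the event with the greatest relationship and greatest severity".

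**The concern.** A table by relationship to study drug needs one rule for choosing the event that represents a subject with repeat events. SAP 9.1 supplies two. The paragraph that defines the table says greatest relationship. The one after it says maximum severity, and names relationship to study medication explicitly. A programmer who follows the second rule builds a different table from one who follows the first.

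The choice matters because the trial was terminated early. All analyses are descriptive, and efficacy is reduced to F-VASI summaries, so the AE tables are a main remaining output. Repeat reactions with mixed attribution are possible. Protocol 5.1.8 asks investigators whether a site reaction is due in whole or part to phototherapy, and Protocol 5.9 provides for application site reactions that recur. A reader of the clinical study report would take the relationship table as the count of subjects with a related event for each term.

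**Working it through.** The documents state no figure on this point, so the check compares the rules and then adds an illustration under stated assumptions.

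**The rules side by side**

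| Source | Output | Event that represents the subject |
|---|---|---|
| SAP 9.1, table description | Relationship to study drug | Greatest relationship |
| SAP 9.1, following paragraph | Summaries showing severity and relationship to study medication | Maximum severity |
| SAP 9.1, table description | Relationship to phototherapy | Greatest relationship |
| Protocol 6.3.1 | AE counts within class or term | Greatest relationship and greatest severity |
| SAP 9.1, overall summary | Subjects with at least one related TEAE | No selection needed |
| SAP 9.1, listings | All AEs | No selection needed |

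Only the study-drug relationship table carries two rules.

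**Worked case.** One subject has two events of the same preferred term: mild, probably related; and severe, unrelated.

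- Greatest relationship: shown as probably related, so 1 related subject.
- Maximum severity: shown as unrelated, so 0 related subjects.
- Overall row for at least one related TEAE: 1 subject under either rule.

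Under the maximum-severity rule the table and the overall row disagree about this subject.

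**Direction.** The relationship of the most severe event can never exceed the greatest relationship among all the subject's events. For every subject, the category shown under maximum severity is therefore the same or lower. The related total can fall or stay equal; it cannot rise.

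**Missing severity.** Suppose a subject has a moderate, likely related event and an unrelated event of the same term with severity missing. The missing value becomes severe, so under the maximum-severity rule the unrelated event represents the subject. An imputation that is cautious for severity then works against caution on causality. It also runs against SAP 6.1.8, which treats missing relationship as related.

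**Ties.** SAP 9.1 has no rule for two events of equal severity and different relationship.

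**Illustration (assumed inputs, not trial data).** Take subjects with exactly two events of one term. Let severities follow proportions s (mild, moderate, severe), let each event be related with probability q, and let everything be independent. Then:

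- P(at least one related) = 1 − (1 − q)² = q(2 − q).
- P(exactly one related) = 2q(1 − q).
- P(the unrelated event is strictly more severe) = (1 − Σs²)/2.

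Among subjects with a related event, the share shown as unrelated under maximum severity is:

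- ties given to the related event: (1 − Σs²)(1 − q)/(2 − q);
- ties broken at random: (1 − q)/(2 − q).

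| Severity mix | 1 − Σs² | q = 0.1 | q = 0.3 | q = 0.5 |
|---|---|---|---|---|
| 60/30/10% | 0.540 | 25.6% | 22.2% | 18.0% |
| 80/18/2% | 0.327 | 15.5% | 13.5% | 10.9% |
| equal thirds | 0.667 | 31.6% | 27.5% | 22.2% |
| any mix, random ties | – | 47.4% | 41.2% | 33.3% |

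For example, with the 60/30/10 mix and q = 0.1: 0.54 × 0.9/1.9 = 25.6%.

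Under greatest relationship the share is 0% by construction. Subjects with a single event of the term are not affected, so the share among all subjects with a related event is smaller. If an investigator tends to attribute a subject's repeat events the same way, it is smaller again.

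**The case against.** The strongest reply is that the SAP already states the right rule where the table is specified. On this view the later sentence is a loosely worded severity rule, since the text that follows ranks severities and imputes a missing one. Alternatively, it covers only displays that cross severity with relationship. Both readings are possible. But a pure severity rule would have no reason to mention relationship to study medication, and SAP 9.1 describes no crossed table: it offers severity or relationship. The text does not settle the matter, and that is the defect.

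Second, Protocol 6.3.1 names both criteria for one event and does not say which prevails when they point to different events. That is correct. It gives no support to maximum severity alone in a relationship table, and SAP 10 lists no such change, but it is less decisive than a plain greatest-relationship rule would be.

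Third, the practical effect may be small. Protocol 5.7.1 makes irradiated-site reactions AEs only if they exceed the expected reaction, need medical intervention or lead to stopping phototherapy. Local tolerability is summarised separately (SAP 9.2). No subject finished the treatment period (SAP 3), which limits repeat events. All of this stands, and it limits the size of the effect without removing the contradiction.

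**Conclusion.** SAP 9.1 contradicts itself on event selection for the class and preferred-term table by relationship to study drug. Followed literally, the maximum-severity sentence shows a subject with a milder related event and a more severe unrelated one as unrelated. The resulting error can go only one way, and the table may not reconcile with the overall row.

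Three stronger conclusions that a reader might draw are not supported:

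- **That the SAP under-counts related TEAEs as a settled choice.** It also states greatest relationship, so under-counting is a risk under one reading.
- **That the phototherapy table is affected.** The maximum-severity sentence names study medication only. The phototherapy table has its own greatest-relationship rule, and its link to the study-drug table points back to the greatest-relationship description.
- **That related events disappear from the report.** The count of subjects with at least one related TEAE is the same under either rule, and the listings show every AE.

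The size is unknown because the documents give no AE counts. The illustrative 11% to 32% (ties to the related event) and 33% to 47% (random ties) apply only to subjects with two events of one term, at least one of them related, under assumed severity mixes and independence. The true effect could be nil. The point is a modest one, worth correcting because the direction is known and the remedy is cheap.

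**What to change.** Replace the maximum-severity sentence in SAP 9.1 with wording such as:

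*Severity tables count each subject once per system organ class and preferred term, at maximum severity. Relationship tables count each subject once per system organ class and preferred term, at the greatest relationship, whatever the severity, with study drug and phototherapy handled separately.*

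Keep the ranking of severities and the missing-severity rule, and tie both to the severity tables. If any table crosses severity with relationship, state how the representing event is chosen there, including ties.

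This agrees with the table description in SAP 9.1 and is compatible with Protocol 6.3.1. It costs one sentence in the SAP, plus one sort key in the table program if the literal rule was coded.
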